Aim3: H1. Motion correction will be performed by realignment of the control and label image series to the M0 image. A structural correlation-based outlier rejection method will be applied to remove artifacts arising from outlier control-label pairs in ASL data. The perfusion-weighted maps will be calculated voxel by voxel from the average of signal differences between labeling and control images. The CBF will be quantified by $(6000 \cdot \lambda \cdot \Delta S \cdot \exp(-PLD/T1, \text{blood})) / (2 \cdot \alpha \cdot T1, \text{blood} \cdot SPD \cdot (1 - \exp(-\tau/T1, \text{blood})))$, where λ is the brain/blood partition coefficient in mL/g, ΔS is perfusion-weighted signal, $T1, \text{blood}$ is the longitudinal relaxation time of blood in seconds, α is the labeling efficiency, SPD is the signal intensity of a proton density-weighted image, and τ is the label duration. pcASL images will be registered to the T1-weighted anatomical image and normalized to MNI space. The CBF maps will be normalized by mean CBF value of GM and a 3D Gaussian filter will be applied. Comparisons will be restricted to rVLPFC and left TPJ ROIs, where 5000 permutations will be generated to identify statistically significant voxels pre- vs post-tDCS, controlling family-wise error rate ($p < 0.05$). H2. Data analysis will focus on (1) behavior assessed by reaction time and accuracy (d') measures from the AX-CPT, and on (2) attend-ignore difference in gamma-band oscillatory power measured from frontocentral electrodes in scalp-recorded ASSR (100-500 ms post-stimulus) as well as during the "preparation" window from 500-1000 ms following "B" trials of the AX-CPT. Spectral power will be measured using Morlet wavelet transforms with minimum width of 5 cycles, will be applied to elongated epochs at logarithmic steps from 4 to 80 Hz across the epoch. Maps of spectral measures will be baseline-corrected using a pre-stimulus baseline adjusted for >3 cycles per frequency to avoid edge effects. Four wavelet measures will be derived: Evoked power, the squared amplitude of oscillations that are phase-locked to stimulus onset; Total power, the average of power on each trial, which includes both evoked and "induced" (non-stimulus locked) responses; Induced power, calculated by removing

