evoked from total power; and phase locking, the degree to which signals are in phase from trial to trial. We are most interested in total power in the AX-CPT, and evoked power ASSR; however, we will examine each of these measures as appropriate. Change scores will be calculated for each dependent variable as the difference between measures taken before and after each arm of the study (Active and Sham). We will compare these difference scores between active and sham arms of the study using repeated measures MANOVA with follow-up univariate RM-ANOVA and paired t-tests as appropriate. H3. Data analysis for H3 will follow the same procedures as H2; however, ASSR in the ignore condition will be the primary dependent variable in this analysis.

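### Aim 3, H2 and H3, leave about 14 outcomes open with no multiplicity rule, and the MANOVA is singular if evoked, total and induced power all enter it on a linear scale

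*SAP*

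**What the plan says.** SAP, Aim 3, H2 names two kinds of outcome. The first is "behavior assessed by reaction time and accuracy (d') measures from the AX-CPT". The second is spectral power in two places: the "attend-ignore difference in gamma-band oscillatory power measured from frontocentral electrodes in scalp-recorded ASSR", and the AX-CPT preparation period, a "window from 500-1000 ms following" the B trials.

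The SAP then says "Four wavelet measures will be derived": evoked power, total power, induced power and phase locking. The third is defined from the first two ("Induced power, calculated by removing" evoked power from total power). Total power is preferred for the AX-CPT and evoked power for the ASSR, but the sentence ends by saying that "we will examine each of these measures as appropriate".

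Pre-post change scores are compared between the active and sham arms "using repeated measures MANOVA with follow-up univariate RM-ANOVA and paired t-tests as appropriate". H3 follows the same procedures, and "ASSR in the ignore condition will be the primary dependent variable in this analysis"; that sentence does not name the wavelet measure.

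For H2 and H3 the SAP gives no significance level, no multiplicity adjustment, no list of variables entering the MANOVA, and no statement that the MANOVA must be significant before follow-up. Family-wise error control is stated only for the voxelwise blood-flow comparison in Aim 3, H1. Neither document gives a sample size.

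**The concern.** The Protocol's Objectives say that the study is to establish whether the intervention modulates its neural target. With an open set of measures and unadjusted follow-up tests, one significant result among many could be read as target engagement. A reader of the results could not tell whether that measure was chosen before or after the data were seen.

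A second, separate problem is computational. One of the four wavelet measures is defined from two others, so a MANOVA that takes all of them may not be computable, or may depend on how the software handles redundancy.

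**Working it through.** The plan gives no error rate or power figure for H2 and H3, so there is none to reproduce.

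**1. Outcome count (from SAP, Aim 3).**
- H2 behaviour: reaction time and d' = 2.
- H2 ASSR, attend minus ignore: 1 contrast x 4 measures = 4.
- H2 AX-CPT preparation window: 1 window x 4 measures = 4.
- H2 total: 2 + 4 + 4 = 10.
- H3 ASSR, ignore condition: 4.
- H2 and H3 together: 10 + 4 = 14.

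This is the plain reading, not a ceiling. Reaction time by trial type, or the separate attend and ignore power in the Protocol's Methods, would add more.

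**2. Error with no gate.** Assume two-sided 5% per test. For m independent tests with every effect null, the chance of at least one false positive is 1 - 0.95^m.
- m = 10: 1 - 0.95^10 = 0.401.
- m = 14: 1 - 0.95^14 = 0.512.
- m = 2 (the two preferred measures alone): 1 - 0.95^2 = 0.0975.

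Correlation lowers these. When the 10 H2 outcomes were simulated with the built-in dependency (15 to 30 per arm, correlation 0 to 0.5), the ungated figure was about 25-37%.

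**3. Error behind a significant MANOVA.** The assumed inputs are 20 per arm, 10 non-degenerate outcomes, a two-sample Hotelling test at 5%, then unadjusted two-sample t-tests.
- Every effect null: the gate opens about 5% of the time, so error is held.
- One true effect of 1.5 SD, correlation 0 to 0.7: at least one of the nine null outcomes is declared in about 23-34% of trials.
- One true effect of 0.8 SD: about 15-17%, because the gate opens less often.

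Once the gate is almost always open, the figure approaches the ungated error of the nine null tests, which is at most 1 - 0.95^9 = 0.370 under independence. Simulation runs differ by a few points; at correlation 0.7 another run put the ungated figure for the nine nulls at about 20%, so the low end is best read as roughly one in five.

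**4. Linear dependence.** Write E, T and I for evoked, total and induced power, with I = T - E. Taking attend minus ignore, or post minus pre, keeps the relation: change in E - change in T + change in I = 0 for every participant. The error matrix is then singular.
- Each four-measure set has rank 3 of 4, so the H2 set has rank 8 of 10.
- This holds for power-scale subtraction with a subtractive baseline.
- With a ratio or dB baseline applied to each measure separately, an example gave rank 4 of 4 and a condition number of about 56: correlated, but invertible.

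The SAP does not say which scale or baseline method applies.

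**The case against.** The strongest case on the other side is that this is a mechanistic study whose SAP already sets priorities: two preferred wavelet measures and a primary variable for H3. On the two preferred measures alone, the independent-test error is 9.75%, not 51%. This stands as partial prioritisation. It does not close the list, because the same sentence reopens it and nothing in H2 is declared primary.

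Several stronger readings are tempting, and the documents do not support them.
- *The singular MANOVA inflates false positives.* It does not. Singularity makes the test non-computable or software-dependent; with a generalised inverse, the gate kept its size at about 4-6% in simulation. The inflation comes from the unadjusted follow-ups and the open list.
- *All 14 outcomes sit behind one MANOVA.* H3 is described as its own analysis, so two MANOVAs is the natural reading.
- *The MANOVA is certain to be singular, or nearly so under log scaling.* The SAP does not commit to entering all four measures together or to a linear scale, and the example on a dB scale was invertible.
- *A real effect would be lost at the gate.* The SAP does not say that there is a gate. The dilution also depends on the correlation: at 20 per arm with one effect of 0.8 SD, the gate opens in about 26% of trials at correlation 0 but 73% at 0.7, against 69% power for one named test. With no sample size stated, power cannot be judged either way.
- *The 40% or 51% is the trial's error rate.* Those figures assume independence and no gate, and must not be combined with figures that assume a gate.

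**Conclusion.** The concern holds in limited form. H2 and H3 open about 14 outcomes with no multiplicity rule. If a significant MANOVA is required first, error is controlled only under the global null; with one large true effect, roughly one trial in five to one in three would also declare a null outcome. If it is not required, the error is about 25-37% for the 10 H2 outcomes under the dependency simulated, with 40% (10 outcomes) and 51% (14 outcomes) as upper-end values.

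These sizes rest on an assumed 5% level, assumed arm sizes, effects and correlations, and the plain outcome count. The absence of strong error control does not depend on them.

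The singularity is a separate, conditional defect: it arises only if evoked, total and induced power enter together on a linear scale with a subtractive baseline.

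This is a worthwhile and inexpensive improvement to the SAP. It does not show that the trial's conclusions would be wrong.

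**What to change.** Replace the open-ended sentence with a closed list built on the SAP's own preferences.
- **H2:** AX-CPT total power in the preparation window; ASSR evoked power, attend minus ignore; d'; and one named reaction-time measure. Compare each between arms, with Holm across the four (ordered thresholds 0.05/4 = 0.0125, 0.05/3 = 0.0167, 0.05/2 = 0.025 and 0.05).
- **AX-CPT band:** name one. The Protocol's Methods specify beta, while the SAP sentence carries gamma wording; reconcile them first.
- **H3:** ASSR evoked power in the ignore condition as the single primary, declared a separate hypothesis. State openly that error is then 5% for each hypothesis, so up to 5% + 5% = 10% across both.
- **Tests:** use between-arm tests. Paired t-tests between arms do not fit the parallel-arm design in the Protocol's Design section.
- **Other wavelet measures:** report as exploratory estimates with confidence intervals and no significance claim.
- **MANOVA:** it need not be dropped. If it is kept, list its variables, leave induced power out, and state the power scale and baseline method.

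The cost is SAP wording only. The downside is that the extra wavelet measures can no longer support confirmatory claims.

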Unique Protocol ID:	STUDY22070009
Brief Title:	Auditory Control Enhancement (ACE) in Schizophrenia (ACES)
Official Title:	Targeting the Auditory Control Network With Auditory Control Enhancement (ACE) in Schizophrenia
Secondary IDs:	R21MH128823 [U.S. NIH Grant/Contract Award Number]

Date: 02/06/2023

Study Protocol

Objectives

Although Auditory Control Enhancement (ACE) shows promise for treating AH, evidence for neural target engagement is needed to move forward with efficacy trials. In alignment with NIMH priorities, we plan to incorporate objective measures that test the delivered dosage and the proposed mechanism of action of the intervention and determine if the intervention target has been modulated. MRI and EEG afford parametric tests of biophysical and neurophysiological target engagement. In the proposed research, we will investigate biological target engagement in two sham-controlled experiments. In this study, we will determine whether tDCS of the auditory control network (rVLPFC anode and left TPJ cathode) leads to alterations in electric field and blood oxygenation level dependent (BOLD) response in the auditory control network during stimulation using Dual-Echo Echo Planar Imaging. Additionally, we will examine the degree to which ACE modifies behavioral and neurophysiological markers of cognitive control.

Design

Participants were randomly assigned to either active/verum or sham/placebo tDCS in a parallel-arm, 2x2 between-subjects repeated-measures design.

Methods

Prior to obtaining informed consent, participants underwent a telephone screening using a standardized script, which took approximately 15 minutes. After consent was obtained, a hearing test using the method of ascending limits (Grayson-Stadler GSI 17 Audiometer) was administered by [name] or trained research staff to rule out hearing loss, as this was essential for the auditory sensation experiment. This test was conducted in the research offices at Western Psychiatric Hospital and lasted about 15 to 30 minutes during the first session. Participants who did not pass the hearing test were advised to contact their primary care provider. Additionally, participants completed the Society of Magnetic Resonance Imaging's standardized MRI screening protocol prior to each MRI visit, which took about 10 minutes.

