Demographic and medical history information was collected using a standard form during the first visit. Clinical and diagnostic assessments included the Structured Clinical Interview for DSM Disorders (SCID), which lasted approximately 1.5 to 2 hours. Additional assessments included the Positive and Negative Syndrome Scale (PANSS), Psychotic Symptoms Rating Scales (PSYRATS), and Global Functioning: Social and Role Scales.

These assessments collectively took about two hours, with PSYRATS administered both before and after ACE.

Neuropsychological testing involved the full MATRICS battery, targeting six cognitive domains affected in schizophrenia, and subtests from the WASI to assess general intelligence. The MATRICS battery took about one hour, and the WASI took approximately 30 minutes. Both were administered before and after ACE.

During the Auditory Control Enhancement (ACE) procedure, participants received transcranial direct current stimulation (tDCS) while performing a simple cognitive task. They were randomly assigned to receive either full-duration tDCS or a 30-second version (sham). [name] randomized participants based on their order of entry into the study. The study was single-blind, with participants unaware of their group assignment. Electrodes were placed over the right ventrolateral prefrontal cortex (anode; F8) and the left temporoparietal junction (cathode; CP5). tDCS sessions, conducted at WPH (Thomas Detre Hall and Oxford), were administered by [name] or trained staff. The current strength was set to 2.0 mA and was delivered for 30 minutes per session using saline-soaked sponge electrodes (10 cm² in size). Stimulation began two minutes before the task to assess discomfort, and skin sensation was checked verbally at least twice during stimulation. Participants were reminded they could withdraw at any time, and electrodes were never placed over the heart, eyes, or ears.

During tDCS, participants performed a cognitive task designed to train attention, working memory, and processing speed, lasting about one hour. The first ACE session involved a circular image with a single radius line, resembling a clock hand. Participants held a button to start each trial and released it when the line reached a target point. The task increased in difficulty by removing visual cues. ACE sessions 2 and 3 utilized simple button-response tasks and assessed reaction time and time estimation, respectively, using only basic shapes and lines.

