EEG testing was led by [name] with support staff utilizing a 32-channel Starstim system. EEG amplifier bandpass was open (DC) to 166 Hz (24 dB/octave rolloff) digitized at 500 Hz. ASSR and AX-CPT stimuli were presented using Presentation software (NeuroBehavioral Systems). Timings of stimuli were confirmed by oscilloscope, and loudness confirmed with a sound meter and artificial ear canal. Sounds were created with NCH Tone Generator and edited in NCH Wavepad (NCH, Australia) and were presented over Etymotic 3A insert earphones. We measured differential 40Hz ASSR gamma power between attend/ignore conditions and beta-band oscillatory power in the AX-CPT as neurophysiological measures of auditory control network function. **ASSR.** Biphasic click trains were presented at 40 Hz (80 db, 500 ms duration, 1000 ms \pm 200 ms ISI). Subjects

once ignored the click trains and watch a silent video, and once listened to the clicks, pressing a button to click train presented at reduced intensity (75 db, 10% of trials) . We recorded 360 trials each under attend/ignore conditions. We assessed 35-45 Hz gamma power in frontocentral electrodes in attend and ignore conditions, as well as the difference between attend/ignore measurements. **AX-CPT** uses a combination of Latin letters as cues and probes following the established A-then-X rule. More specifically, the rule for the AX- is that 'X' is the target when directly preceded by the letter "A" trials, whereas a letter in any other sequence is a nontarget (e.g., AY, BX, and BY trials, where a B is any non-A cue, and a Y is any non-X probe). The AX and BX trials both require the representation and maintenance of the cue, or the goal of the task, to respond appropriately. BX trials tend to be the most sensitive to impairments in the ability to maintain the goal representation. That is, maintenance of the B cue is required to overcome the prepotent target response to the X on the trials when it does not follow an A. The most difficult trial is AY, given that goal focused maintenance of the A cue should produce a high expectancy of a subsequent X probe and preparation of a target response, resulting in increased errors or slowing on AY trials. 450 trials were presented in 6 blocks of 75 trials. The cue was presented for 500 ms with ISI of 1000 ms. Cognitive control was indexed by prefrontal beta-band activity following attention-alerting "B" trials. EEG was conducted both before and after ACE.

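### H2 and H3 compare raw change scores between arms; if the parallel design is confirmed, adjusting for the pre-ACE value would usually be more precise, at small cost

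*SAP*

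**What the plan says.** The SAP, Aim 3 H2, names the outcomes as "behavior assessed by reaction time and accuracy (d') measures from the AX-CPT", the attend-ignore difference in ASSR power, and power in the AX-CPT preparation window. On the analysis it says: "Change scores will be calculated for each dependent variable as the difference between measures taken before and after each arm of the study". The difference scores are then compared between active and sham "using repeated measures MANOVA with follow-up univariate RM-ANOVA and paired t-tests as appropriate". H3 inherits this: "Data analysis for H3 will follow the same procedures as H2; however, ASSR in the ignore condition will be the primary dependent variable".

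No covariate for the pre-treatment value appears anywhere. The baseline correction mentioned under H2 is a pre-stimulus correction of the EEG spectra, not an adjustment for the pre-ACE measurement.

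The Protocol, Methods, describes ASSR and AX-CPT as parts of the EEG session and states: "EEG was conducted both before and after ACE". Every H2 and H3 outcome therefore has a pre-ACE value. The Protocol, Design, assigns participants to active or sham "in a parallel-arm, 2x2 between-subjects repeated-measures design".

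**The concern.** Subtracting the baseline fixes the slope of the post value on the pre value at 1. With equal pre and post variance the actual slope is rho, which is below 1 for any imperfectly repeatable measure. The subtraction therefore over-corrects and carries baseline noise into the arm comparison. It also leaves the estimate tied to whatever baseline difference chance produces.

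At stake is precision on the behavioural and neurophysiological outcomes. The baseline data that would recover it are already in the schedule, so the remedy needs no new measurement.

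**Working it through.** **Inputs from the documents.** Two arms, parallel (Protocol, Design); pre and post values for each outcome (Protocol, Methods); change scores without a covariate (SAP, Aim 3 H2 and H3). The plan gives no sample size, power, effect size, SD or pre-post correlation, and no significance level for H2 or H3, so it has no figure to reproduce.

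**Assumptions.** 1:1 allocation, n per arm, equal pre and post variance s², correlation rho. For the power illustration: true effect of 0.8 raw SD, two-sided 0.05.

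**Large-sample variance of the arm effect**, in units of (2/n)s²:

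- Change score: 2(1 − rho)
- ANCOVA: 1 − rho²
- Ratio, ANCOVA to change: (1 − rho²) / [2(1 − rho)] = (1 + rho)/2

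| rho (assumed) | Change | ANCOVA | Ratio | Extra participants the change score needs (1/ratio − 1) |
|---|---|---|---|---|
| 0.3 | 1.40 | 0.91 | 0.65 | 54% |
| 0.5 | 1.00 | 0.75 | 0.75 | 33% |
| 0.7 | 0.60 | 0.51 | 0.85 | 18% |
| 0.9 | 0.20 | 0.19 | 0.95 | 5% |

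Comparing post values alone has variance 1 in these units, so below rho = 0.5 the change score is noisier than ignoring the baseline.

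**Small-sample cost.** Estimating the slope multiplies the ANCOVA variance by 1 + 1/(2n − 4). With n = 10 this is 1 + 1/16 = 1.0625. The ratio becomes 0.69, 0.80, 0.90, 1.01 and 1.04 at rho 0.3, 0.5, 0.7, 0.9 and 0.95. ANCOVA stops gaining at rho = 2/1.0625 − 1 = 0.88. With 15 and 20 per arm the break-even is about 0.93 and 0.95.

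**Simulated power**, 20,000 replicates, 15 per arm, change score against ANCOVA: 44% and 58% at rho 0.3; 56% and 66% at 0.5; 78% and 83% at 0.7; 99.8% for both at 0.9. With no true effect, both rejected in about 5% of replicates.

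**Chance baseline imbalance.** Given an observed baseline difference d between arms, the expected change-score estimate is the true effect − (1 − rho)d. The simulation with 15 per arm gave slopes on d of −0.70, −0.50, −0.29 and −0.10 at rho 0.3, 0.5, 0.7 and 0.9; the ANCOVA slopes were within 0.01 of zero. For scale, with 15 per arm the SD of d is √(2/15) = 0.37 raw SD. At rho 0.5 an imbalance of that size moves the change-score estimate by 0.5 × 0.37 = 0.18 raw SD.

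**The case against.** The strongest objection is that the comparison may not be parallel at all. The SAP speaks of measurements around each arm and plans paired t-tests between active and sham, which fits participants who receive both conditions. In that case neither the two-arm regression nor the ratios above apply as written. This stands as a condition. The Protocol, in Design and Methods, describes assignment to one condition or the other, but the two documents must be reconciled before any model is fixed.

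It could also be said that a repeated-measures analysis already uses the baseline. It does not in the sense meant here: with one pre and one post value, the arm-by-time test is the change-score test.

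Replacing the multivariate test with one model per outcome leaves multiplicity open. That is fair, and the revised text should deal with it.

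A reader might infer three stronger points, none of which the documents support:

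- **That the planned analysis is biased.** Over repeated proper randomisations change scores are unbiased. The shift is conditional on the observed baselines, and the false-positive rate was about 5% for both methods. The Protocol says only that staff "randomized participants based on their order of entry into the study"; if allocation was not properly random, baseline adjustment would not cure that.
- **That the gain is known to be large.** Neither the arm sizes nor the repeatability of these measures is stated. The attend-ignore outcome is itself a difference, which may lower its correlation, but reaction time, d' and the ignore-condition ASSR of H3 are not attend-ignore differences.
- **That change scores lose participants.** Complete-case loss belongs to the multivariate test, not to the change score. The SAP also plans univariate follow-up, and a participant without a post value drops out of this ANCOVA too.

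**Conclusion.** The point holds as an efficiency and robustness improvement, not as an error that invalidates H2 or H3. Under a randomised parallel design with equal pre and post variance, ANCOVA lowers the large-sample variance by 35%, 25%, 15% and 5% at assumed rho of 0.3, 0.5, 0.7 and 0.9. It also removes the linear effect of chance baseline imbalance. The gain is not free: with around 10 per arm and rho of 0.9 or more, variance rises by about 1–4%. How much this trial would gain cannot be derived from the documents, and the conclusion depends on the parallel design being confirmed.

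**What to change.** 1. Reconcile the SAP's paired t-tests and per-arm change wording with the parallel-arm design in the Protocol.
2. If the design is parallel, replace the change-score comparison in Aim 3 H2 and H3 with text such as: *For each outcome, the post-ACE value will be regressed on arm (active or sham) and the pre-ACE value of the same measure. The arm coefficient will be reported with its 95% confidence interval. Change scores will be shown descriptively by arm.*
3. State how the several H2 outcomes are ordered or adjusted, since separate models replace the multivariate test.

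The cost is SAP wording, plus one error degree of freedom and an estimated slope per model (with 10 per arm, 17 error degrees of freedom instead of 18). No new data are needed.

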| | |
|---------------------|---|
| Unique Protocol ID: | STUDY22070009 |
| Brief Title: | Auditory Control Enhancement (ACE) in Schizophrenia (ACES) |
| Official Title: | Targeting the Auditory Control Network With Auditory Control Enhancement (ACE) in Schizophrenia |
| Secondary IDs: | R21MH128823 [U.S. NIH Grant/Contract Award Number] |

Date: 02/06/2023

Statistical Analysis Plan

Aim 1: H1. We will use General Linear Model (GLM) in SPM12 to assess the parametric modulation of 2nd -echo phase and magnitude data with the applied tDCS current as a regressor (as in Jog, Wang, et al., 2020). Phase data provide maps of tDCS-induced current tangential to the static (Bz) magnetic field of the MRI. Magnitude data provide BOLD response. We will test spatial correlation between the measured magnetic field and tDCS current modeled by SIMNIBS to assess overlap with target areas in rVLPFC and left TPJ.

Aim 2: H1. we will calculate retention, blinding, and acceptability scores with benchmarks of success being >80% study completion, high-moderate acceptability rating, and no-greater-than-chance ability to identify study condition. Additionally, t-tests will be used to compare acceptability between ACE and sham sessions.

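### The Aim 3 change-score MANOVA uses only participants with both visits and every entered outcome; separate baseline-adjusted models would use the data better

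*SAP*

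**What the plan says.** The SAP, Aim 3 H2, defines the outcome form: "Change scores will be calculated for each dependent variable", each being the pre-to-post difference around an arm of the study. The arms are then compared "using repeated measures MANOVA with follow-up univariate RM-ANOVA and paired t-tests as appropriate". H3 inherits this: "Data analysis for H3 will follow the same procedures as H2", with ASSR in the ignore condition as its primary variable.

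H2 names at least four dependent variables. Two are behavioural: "behavior assessed by reaction time and accuracy (d') measures from the AX-CPT". Two are EEG measures: the "attend-ignore difference in gamma-band oscillatory power measured from frontocentral electrodes in scalp-recorded ASSR", and power in the AX-CPT preparation window. The Protocol (Methods, EEG) places the EEG session once before and once after ACE.

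On completion, the SAP gives only the Aim 2 H1 feasibility criterion, "benchmarks of success being >80% study completion". Neither document defines an analysis population, a rule for analysing participants as randomised, or any handling of missing data.

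**The concern.** A change score does not exist unless both visits yield a usable value. A standard MANOVA also omits anyone who lacks one of the variables entered together. Nothing in the plan overrides either default, so the main H2 comparison would rest on participants complete on all entered outcomes, and a gap in one task would discard good data from another.

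Precision is at stake first. Bias comes second: if the reasons for missing data differ between full-duration and sham stimulation, the participants left in the analysis are no longer the groups that were randomised. The documents state no sample size, so no margin for such loss can be seen.

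**Working it through.** The plan gives no sample size, dropout allowance or retained share, so there is no figure to reproduce. Everything below is illustration on stated assumptions.

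**Inputs.**
- Completion c = 80%, the lower edge of the Aim 2 benchmark, with 90% and 95% for comparison (assumed).
- Unusable share m = 3%, 5% or 10% per recording (assumed).
- Recordings: two tasks (ASSR, AX-CPT) at two visits, so four. The attend and ignore ASSR runs of a visit count as one.

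**Retained share of those randomised.**
- MANOVA, independent failures: c × (1 − m)⁴
- MANOVA, failures fully shared by both tasks within a visit: c × (1 − m)²
- Single-task outcome needing both visits: c × (1 − m)²

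| c | m | MANOVA, independent | MANOVA, shared | Single-task outcome |
|---|---|---|---|---|
| 0.80 | 0.03 | 0.80 × 0.97⁴ = 71% | 0.80 × 0.97² = 75% | 75% |
| 0.80 | 0.05 | 0.80 × 0.95⁴ = 65% | 0.80 × 0.95² = 72% | 72% |
| 0.80 | 0.10 | 0.80 × 0.90⁴ = 52% | 0.80 × 0.90² = 65% | 65% |
| 0.90 | 0.05 | 0.90 × 0.95⁴ = 73% | 0.90 × 0.95² = 81% | 81% |
| 0.95 | 0.05 | 0.95 × 0.95⁴ = 77% | 0.95 × 0.95² = 86% | 86% |

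At c = 80% and m = 5%, the loss due to the MANOVA itself is therefore between 0 and 7 percentage points. At the 7-point end the standard error is 1/0.95 = 1.05 times that of the single-outcome analysis.

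**Change score against baseline adjustment.** With equal pre and post variance σ², pre-post correlation ρ and the same participants, the arm contrast has variance proportional to 2σ²(1 − ρ) for change scores and σ²(1 − ρ²) after baseline adjustment. The ratio is (1 + ρ)/2:
- ρ = 0.4: 0.70, a 30% reduction
- ρ = 0.6: 0.80, a 20% reduction
- ρ = 0.8: 0.90, a 10% reduction

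**Bias.** A simulation with no true effect used 1,000,000 per arm, ρ = 0.6, baseline SD 1 and SD of change √(2 − 2 × 0.6) = 0.89. It gave these false arm differences, in baseline SD units:

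| Missingness (sham / active) | Complete-case change score | Baseline-adjusted |
|---|---|---|
| Completely random, 20% / 20% or 10% / 30% | 0.00 | 0.00 |
| Related to baseline, same in both arms | 0.00 | 0.00 |
| Related to change, same in both arms | 0.00 | 0.00 |
| Random 20% / low-baseline 20% | −0.10 | 0.00 |
| Related to baseline, 10% / 30% | −0.05 | 0.00 |
| Related to change, 10% / 30% | 0.10 | 0.09 |
| Random 20% / low post value 20% | 0.10 | 0.16 |

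Unequal dropout rates alone caused no bias. It appeared only where missingness was tied to the measurements in a way that differed by arm. Baseline adjustment removed it when the link was to baseline, and not when it was to the post value or the change.

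**The case against.** A reader might infer that one bad recording removes a participant from every outcome by the plan's own rule. The SAP does not say so. Casewise omission follows from the named method in its standard form, and the SAP never says that all outcomes enter one MANOVA. The univariate follow-ups need only their own outcome, and H3 has a single primary variable. This narrows the point but does not remove it. The multivariate test comes first for H2, both visits are needed throughout, and even a MANOVA restricted to the EEG measures would combine ASSR with AX-CPT.

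A reader might also infer that the plan accepts a 20% loss. The ">80% study completion" figure is a feasibility benchmark under Aim 2, not an attrition allowance for Aim 3, so 80% is used here only as a lower edge.

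Independence of failures is doubtful. Both tasks are recorded on one EEG system at each visit, so a missed session or poor recording would often affect both. If failures are fully shared, the MANOVA loses no more than a single-task outcome does. This objection stands, and is why a range is given.

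Finally, a mixed model with one pre and one post value adds little for participants with no post value and relies on data missing at random. Dropping the MANOVA also gives up a single joint test. Both objections stand and shape the fix.

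**Conclusion.** The point holds as a weakness in the choice of analysis, mainly a matter of precision. At 80% completion and 5% unusable data per recording, the MANOVA keeps 65% to 72% of those randomised, depending on how far failures are shared within a visit, against 72% for a single-task outcome. Higher completion raises all these shares. Separately, change scores forgo a variance reduction of about 30% to 10% at correlations of 0.4 to 0.8, even with no missing data.

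It would be tempting to say that the arm comparison is biased. The documents do not support that: they give no missingness by arm, and the simulated bias of about 0.05 to 0.10 baseline SD needed a mechanism that differed between arms. The simulation had no true effect, so it does not address distortion of a real one. Completion, unusable rates, correlation and equal variances are assumptions, not document figures.

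The retained shares also assume parallel arms. If each participant received both conditions, complete data would need more sessions and the loss would be larger. The SAP should be changed, but nothing here shows the comparison to be invalid.

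**What to change.** 1. Reconcile the design. The Protocol (Design) describes parallel arms compared between subjects; SAP Aim 3 H2 speaks of measures before and after each arm and plans paired t-tests, which suggest a within-subject comparison. The model depends on which applies.
2. Assuming parallel arms, analyse each H2 and H3 outcome separately with baseline adjustment: a mixed model with pre and post values as responses, a common baseline mean and an arm-by-visit term. Include all randomised participants with any measurement, in the arm assigned.
3. Control multiplicity across the outcomes, for example by Holm, or keep the MANOVA as a supportive test.
4. Report missingness by arm for each outcome and visit.
5. Keep the complete-case change-score analysis as a sensitivity analysis, and add one for data not missing at random, since baseline adjustment does not protect against that.

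The cost is SAP wording, a multiplicity adjustment, slightly more analysis work and reliance on missing at random given the observed values. No new data are needed.
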